STUDY PROTOCOL

1. Title of the Study

Clinical Profile of Appendicitis and Comparative Study of Harmonic Scalpel (Seal and Cut) Versus Suture Ligation of the Base of Appendix During Laparoscopic Appendectomy

2. Protocol ID & Registration

Protocol ID: GSVM/GENSURG/APP/2025

ClinicalTrials.gov Identifier (NCT Number): [To be added]

Trial Registration Registry: ClinicalTrials.gov

3. Principal Investigator

Name: [name]

Designation: Principal Investigator

Affiliation: Department of General Surgery, GSVM Medical College, Kanpur, India

Email: [contact]

[contact]

4. Research Guide / Senior Author

Name: Dr. [name]

Designation: Professor & Head

Department: General Surgery, GSVM Medical College, Kanpur

5. Background and Rationale

Acute appendicitis is a common surgical emergency. Laparoscopic appendectomy is widely accepted, with secure closure of the appendix base being a critical step. The harmonic scalpel offers an energy-based alternative to traditional suturing. This study aims to compare outcomes between these two techniques.

6. Study Objectives

Primary Objective:

- To compare operative time between harmonic scalpel and suture ligation techniques.

Secondary Objectives:

- To evaluate postoperative complications (leak, ileus, SSI)
- To assess hospital stay duration
- To document appendix position intraoperatively

7. Study Design

Study Type: Interventional (Clinical Trial)

Allocation: Randomized (computer-based)

Interventional Model: Parallel Assignment

Masking: Single (Participant)
Number of Arms: 2
Primary Purpose: Treatment

8. Participants

Sample Size: 60 patients (30 per group)

Inclusion Criteria:

- Age 15–60 years
- Diagnosed with uncomplicated acute appendicitis
- Consent to participate

Exclusion Criteria:

- Perforated/gangrenous appendix
- Pregnancy
- Coagulopathy or severe comorbid illness

9. Interventions

Arm A: Harmonic Scalpel Group (Experimental)

Laparoscopic appendectomy using harmonic scalpel to seal and divide appendix base.

Arm B: Suture Ligation Group (Active Comparator)

Laparoscopic appendectomy with intracorporeal suture ligation of appendix base.

10. Outcome Measures

Primary Outcome:

- Operative time (in minutes)

Secondary Outcomes:

- Position of appendix (intraoperative)
- Postoperative leak (within 7 days)
- Postoperative ileus (within 3 days)
- Surgical site infection (within 30 days)
- Hospital stay (in days)

11. Ethical Considerations

Approved by Institutional Ethics Committee, GSVM Medical College

Informed written consent will be obtained from all participants

Trial will be registered with ClinicalTrials.gov

12. Data Sharing Statement

De-identified individual data will be shared upon request for secondary analysis after 6 months of publication.

13. Timeline

Study Start: [April 2024]

Estimated Completion: [e.g., July 2025]

14. Funding and Support

No external funding. Supported by institutional resources.

Date- 01/05/2025

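### The complication outcomes are only leak, ileus and SSI, each in its own window, so bleeding, other-cause reoperation or readmission, and late leak or ileus go uncaptured

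*Protocol*

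**What the plan says.** Section 6 of the protocol gives operative time as the primary objective. The safety objective, one of the secondary ones, is "To evaluate postoperative complications (leak, ileus, SSI"). The bracket has no wording such as 'including' or 'other'.

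Section 10 turns this into three separate outcomes, each with its own window: "Postoperative leak (within 7 days"), "Postoperative ileus (within 3 days") and "Surgical site infection (within 30 days"). The other secondary outcomes are the position of the appendix and "Hospital stay (in days").

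Section 9 describes the experimental arm as "Laparoscopic appendectomy using harmonic scalpel to seal and divide appendix base" and the comparator as intracorporeal suture ligation of the base. Section 8 sets 30 patients per group. The protocol has no adverse-event or safety-reporting section. It does not mention bleeding, reoperation, readmission, an overall complication outcome or a severity grade.

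**The concern.** The objective speaks of postoperative complications in general, but the outcomes admit only three kinds, two of them over short windows. The trial compares two ways of closing the appendix base, a step that Section 5 itself calls critical. Some harm after either technique could first show as bleeding, a return to theatre or a readmission, or as a leak or ileus recognised after its window has closed. If the plan is followed as written, none of these need be recorded as a complication.

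At stake is the completeness of the safety picture beside the operative-time result. A reader of the report could take three low event counts as the whole of the postoperative harm when more serious events had simply not been asked for. The choice of outcomes is fixed in the protocol. An analysis plan cannot tabulate events that nobody was told to collect.

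**Working it through.** **1. Reading the lists against each other.** Sections 6 and 10 agree on the same three events, so there is no contradiction between them. The question is which patients fall outside all three. The table takes patients with a single event.

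| Only event | Leak (7 d) | Ileus (3 d) | SSI (30 d) | Hospital stay |
|---|---|---|---|---|
| Bleeding, index admission | no | no | no | may lengthen, cause not shown |
| Reoperation for another cause, index admission | no | no | no | may lengthen, cause not shown |
| Readmission for another cause | no | no | no | not stated whether readmission days count |
| Leak first evident after day 7 | no | no | no | as above |
| Ileus first evident after day 3 | no | no | no | as above |
| Bowel obstruction by day 3 | no | possibly, as ileus is undefined | no | may lengthen |
| Bowel obstruction after day 3 | no | no | no | as above |
| Reoperation or readmission for leak by day 7 or SSI by day 30 | through its cause | no | through its cause | as above |

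The last row and the early-obstruction row limit the gap. SSI is also undefined, so an intra-abdominal abscess might be counted there. The other rows are the gap.

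**2. How likely is at least one such patient?** The documents give no rate, so the rate p of a patient with only an unlisted event is assumed over a range. The group sizes come from Section 8. The chance of at least one is 1 − (1 − p)^n.

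| Assumed p | n = 30 (one arm) | n = 60 (all) | Expected among 60 (60 × p) |
|---|---|---|---|
| 1% | 26.0% | 45.3% | 0.6 |
| 2% | 45.5% | 70.2% | 1.2 |
| 3% | 59.9% | 83.9% | 1.8 |
| 5% | 78.5% | 95.4% | 3.0 |

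**3. What could 30 per arm show about such events?** With 0 events in 30, the one-sided 95% upper limit for the true rate is 1 − 0.05^(1/30) = 9.5%, and the upper end of the two-sided 95% interval is 1 − 0.025^(1/30) = 11.6%. So even an arm with no event is compatible with a rate near 10%.

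For a comparison, take a two-sided Fisher test at an assumed 5% level, with all events in one arm:
- 5 versus 0: p = 2 × C(30,5)/C(60,5) = 2 × 142,506/5,461,512 = 0.052.
- 6 versus 0: p = 2 × C(30,6)/C(60,6) = 2 × 593,775/50,063,860 = 0.024.

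At least 6 events against none (6/30 = 20% of an arm) would be needed. The expected total in both arms under the assumed rates is 0.6 to 3. The added items can make events visible, but they cannot support a conclusion about which technique is safer.

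**The case against.** The strongest reply is that this is an omission and not an error. The two sections agree, the primary objective is operative time, and a list of secondary outcomes does not say that other adverse events go unrecorded. Case-record forms may collect them, and investigators may mention them. Failure to close the base is leak, which is listed. A return to theatre may show in hospital stay. Much of this stands, and it keeps the point at a modest grade. It does not remove the point: the protocol as written requires no such recording, and hospital stay gives no cause.

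Three stronger readings are tempting and are not supported:

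- **That such patients would be scored free of complications.** The protocol defines no overall complication rate and no complication-free status. It has three separate outcomes, and each would be correctly recorded as absent.
- **That excluding "Coagulopathy or severe comorbid illness" shows the plan regards bleeding as a risk of the technique.** This is one entry criterion, listed beside severe illness. It says nothing about a difference between arms and, if anything, removes the patients most prone to bleed.
- **That the trial would miss a real arm difference in serious harm.** No passage gives a rate or reason to expect one, and 30 per arm could not establish one.

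Nor should reoperation and readmission be called free of judgement. Only the participant is masked (Section 7), and unmasked staff decide on both. Whether they happened is easy to record, but the decision to do either is open to influence.

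**Conclusion.** The point holds as incomplete capture of harm. Postoperative bleeding, reoperation or readmission for a cause other than the listed events, and leak or ileus first evident after its window would appear in no complication outcome. Hospital stay and an undefined ileus category cover a small part of this.

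On assumed rates of 1% to 5%, which are not from the documents, 0.6 to 3 such patients would be expected among 60. The conclusion about the lists rests on the text alone and does not depend on those rates. The primary outcome and the three named outcomes are unaffected. It is an improvement to consider, not a fault that undermines the trial.

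**What to change.** Keep leak, ileus and SSI as they are. Add to Sections 6 and 10, by arm and with cause:

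- any postoperative complication within 30 days of surgery, as the number of patients with at least one, with the worst grade on a named, published severity scale;
- reoperation within 30 days;
- readmission within 30 days;
- postoperative bleeding within 30 days.

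Thirty days is already the SSI horizon, so no longer follow-up is needed. Report counts with confidence intervals, descriptively, without a claim of difference or of equal safety.

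Section 13 gives a start of April 2024 and the document is dated 01/05/2025, which is later on either reading of the date. Some patients have therefore probably been treated. The amendment should declare these items as added after enrolment began, and for patients already treated they should be completed from records in the same way in both arms.

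The cost is a short amendment, a few case-record fields, some retrospective completion and a few more secondary tables. No added patients or tests are needed. Records may miss readmissions to other hospitals, and the report should say so.

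### Does the exclusion of a perforated or gangrenous appendix let an unmasked surgeon drop allocated patients and so bias operative time?

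*Protocol*

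**What the plan says.** Section 8 includes patients "Diagnosed with uncomplicated acute appendicitis" and excludes "Perforated/gangrenous appendix", next to pregnancy, coagulopathy and severe comorbid illness. It does not say whether the state of the appendix is judged before surgery or at laparoscopy. Section 7 describes allocation only as "Allocation: Randomized (computer-based", with no time point, and gives "Masking: Single (Participant" as the masking, so the surgeon is not masked. The planned size is 60 patients, 30 per group. The primary outcome in Section 10 is "Operative time (in minutes". Sections 6 and 10 also have the position of the appendix recorded during the operation. Section 9 describes the two arms by how the appendix base is dealt with.

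**The concern.** An exclusion applied after allocation, by someone who knows the arm and on a finding related to the outcome, is a classic way to spoil a randomised comparison. The ingredients seem to be present. Perforation or gangrene may be recognised only once the appendix is seen, the surgeon must know the arm in order to operate, and complicated cases plausibly take longer. If more such patients were dropped from one arm, the mean operative time of that arm would fall for reasons unrelated to the technique. If no operative time were recorded for them, no analysis could fully repair the loss. The time at which the arm is revealed is also a matter of trial conduct, which an analysis plan cannot set afterwards.

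**Working it through.** **What the text supports.** Set side by side, the inclusion criterion asks for an uncomplicated diagnosis and the exclusion criterion names its opposite. Read naturally, both are entry criteria applied before a patient joins the trial. The protocol contains no sentence that allows, describes or foresees removal after allocation. It does not rule it out either.

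For a bias in operative time, all of the following must hold:

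1. The condition is found only at laparoscopy, in a patient entered as uncomplicated.
2. The arm has already been allocated.
3. The patient is then removed rather than kept.
4. Removal is more frequent in one arm.
5. Complicated cases take longer.

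None of the five is stated in the document. For the fourth, no reason is apparent why the judgement should lean towards one arm, so the bias has no predictable direction.

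**Size, as an illustration only.** The protocol gives no SD, effect size or complication rate, so the sample size cannot be reproduced and every input except 30 per arm is assumed:

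- 30 allocated per arm, no true difference, pooled t-test at two-sided 0.05
- share complicated π = 10% or 20%
- delay δ = 1 or 2 within-stratum SD
- complicated cases dropped with probability q in a given arm

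The mean excess time left in an arm is f(q) = δπ(1 − q)/(1 − πq), and the bias is f(q_A) − f(q_B). For π = 0.2, δ = 2, with 0% v 50% dropped: f(0) = 0.400, f(0.5) = 0.2/0.9 = 0.222, bias 0.178. With 25% v 75% dropped: 0.3/0.95 − 0.1/0.85 = 0.316 − 0.118 = 0.198.

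Bias in within-stratum SD, and simulated type I error (200,000 trials per cell):

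| π, δ | 0% v 50% dropped | 25% v 75% dropped | 0% v 100% dropped |
|---|---|---|---|
| 10%, 1 | 0.047; 5.3% | 0.050; 5.3% | 0.100; 6.3% |
| 10%, 2 | 0.095; 6.1% | 0.100; 6.2% | 0.200; 9.7% |
| 20%, 1 | 0.089; 6.1% | 0.099; 6.3% | 0.200; 10.3% |
| 20%, 2 | 0.178; 8.1% | 0.198; 8.9% | 0.400; 21.7% |

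The partly unequal patterns mean 30 × 0.1 × 0.5 = 1.5 to 30 × 0.2 × 0.5 = 3 more patients lost in one arm on average. Six of those eight cells are at or below 6.3%. If all complicated cases are dropped in both arms, the bias is 0 and the error 5%. The difference detectable with 80% power then hardly moves when complicated cases are 1 SD slower: 0.77 if kept v 0.78 if dropped (10%), and 0.79 v 0.83 (20%). It improves when they are 2 SD slower: 0.86 v 0.78, and 0.94 v 0.83.

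**What a change would reach and cost.** The timeline runs from April 2024 to July 2025 (16 months, dates in brackets), and the document is dated 01/05/2025. With even accrual (assumption) and the date read day-first, 3/16 × 60 = 11 patients remain, or 2/15 × 60 = 8 if the last month is follow-up. Read month-first, it is 7/16 × 60 = 26, or 6/15 × 60 = 24. If 10% to 20% were screened out at inspection, the day-first numbers would need 8/0.9 = 9 to 11/0.8 = 14 consents, and the month-first numbers 24/0.9 = 27 to 26/0.8 = 33.

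**The case for a change.** The best case for a change is that the timing of the reveal belongs in the protocol, and that the protocol makes a late reveal feasible. As described, the arms differ only at the appendix base, and the position of the appendix is recorded intraoperatively anyway, so the arm need not be known before the appendix has been seen. The uncomplicated diagnosis required at entry does not say what happens when the operative finding differs. The stakes can also be made to look larger: a normal approximation with 30 analysed per arm, up to 30% complicated and a delay of 1.5 SD gives a bias of 0.45 SD and a type I error of 41% if one arm drops every such case and the other none.

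Part of this stands. The timing is unstated, the surgeon is unmasked, and an analysis plan cannot move the reveal. But the 41% shows only that the size is set by what one assumes. Feasibility is partly inferred too, since Section 9 does not say that all other steps are the same in both arms. Allocation during the operation also needs instruments for both techniques at hand. It may add a pause to operative time itself, and the protocol does not say when that clock starts or stops. Allocation before or during surgery is a fair trade-off, and the protocol has not chosen wrongly by leaving it unstated. The remaining protection, keeping allocated patients in their arm and reporting removals by arm with reasons, is commonly left to the SAP.

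**Conclusion.** No change to the plan follows. What remains is missing detail: the protocol does not say when the state of the appendix is judged relative to allocation. It states nothing wrong on this point and contradicts nothing, and following it as written is not shown to give a worse result. A bias would arise only if patients were removed after allocation and removals differed by arm. Under the assumed inputs, partly unequal removal gives 0.05 to 0.20 within-stratum SD and a type I error of 5% to 9%; the extreme of 22% needs the worst assumptions together. These figures are illustrations and say nothing about what happens in this trial. If allocation already follows inspection, the risk is absent. If it does not, a sensible analyst would keep allocated patients with a recorded operative time in their arm and list any removals by arm. The assessment rests on the natural reading of Section 8 as entry criteria and on the absence of any sign that removals would differ by arm.

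### Does the trial need a base-closure time because its arms differ only at the appendix base?

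*Protocol*

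**What the plan says.** The title (section 1) describes a "Comparative Study of Harmonic Scalpel (Seal and Cut) Versus Suture Ligation of the Base of Appendix". Section 5 describes laparoscopic appendectomy as widely accepted, "with secure closure of the appendix base being a critical step".

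Section 6 gives one primary objective: "To compare operative time between harmonic scalpel and suture ligation techniques". Section 10 matches it with one primary outcome, "Operative time (in minutes". The five secondary outcomes are appendix position, leak, ileus, surgical site infection and hospital stay. Neither the base step nor any other step is timed separately.

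Section 9 defines Arm A as "Laparoscopic appendectomy using harmonic scalpel to seal and divide appendix base" and Arm B as "Laparoscopic appendectomy with intracorporeal suture ligation of appendix base". Section 7 states randomised allocation and "Masking: Single (Participant". Section 8 sets 60 patients, 30 per group.

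**The concern.** The experimental contrast is confined to one step, but the clock, on the usual reading of operative time, runs for the whole operation. Access, dissection and wound closure are common to both arms. Their variation adds noise to the comparison, and a modest saving at the base could be lost in it. A single total per patient also cannot locate a difference within the operation. Section 9 does not say whether the harmonic scalpel is used for other steps; if it were, and in Arm A only, total time would combine that use with base closure.

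At stake would be a null result that hides a real saving at the base, or a positive one whose source is unclear. No analysis plan can recover an interval that nobody recorded, so the point cannot be set aside merely because the SAP is not at hand.

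**Working it through.** **1. Does the outcome answer the question asked?** The section 6 objective and the section 10 primary outcome are the same quantity. The title names the techniques being compared; it does not say that the time to be compared is that of the base step alone. Section 5 calls closure critical because it must be secure, which concerns safety and not speed, and leak within 7 days is already a secondary outcome. With computer-based randomisation, the difference in mean operative time is an unbiased estimate of the effect of allocation to one technique or the other. The shared steps add variance, not bias.

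**2. How much precision is lost?** The protocol gives no SD, target difference, alpha or power, so there is no figure to reproduce. At two-sided 0.05 and 80% power (both assumed), the detectable difference with 30 per arm is (1.96 + 0.84) × √(2/30) ≈ 0.72 SD of total time.

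Power below is for the two-sample t-test at two-sided 0.05, with n = 30 per arm, 58 degrees of freedom and noncentrality (difference/SD) × √(30/2) = 3.87 × difference/SD. All differences and SDs are assumed.

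| Saving (min) | Total-time SD 10 | SD 15 | SD 20 |
|---|---|---|---|
| 4 | 33% | 17% | 12% |
| 8 | 86% | 53% | 33% |
| 12 | over 99% | 86% | 63% |

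For an interval covering only the base step, with assumed SD 3, 4 or 5 minutes, a 4-minute saving has over 99%, 97% or 86% power. The contrast is large if the saving is small and the total varies widely. It largely disappears if the saving is 12 minutes and the SD is 10 or 15. Nothing in the document says which case applies. The step figures also assume one SD for a device arm and a hand-suturing arm.

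**3. Could a step interval be measured alike in both arms?** The two techniques do not begin with the same event. A start at first application of the device in one arm and first needle entry in the other leaves out introducing and loading the needle, which is part of the time the suture technique takes. Such an interval would drop part of the contrast it is meant to isolate, while total time keeps it. The operating team, which is not masked, would also be timing a finer event.

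**4. How many patients could still be timed?** Section 13 gives "Study Start: [April 2024" in brackets and a bracketed estimated completion of July 2025. The protocol is dated 01/05/2025, which can be read two ways. Assume even accrual from a start between 1 and 30 April 2024 to an end between 1 and 31 July 2025.

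- Read as 1 May 2025: elapsed fraction 0.80 to 0.87; × 60 = 48 to 52 patients already operated on; 8 to 12 left, or 4 to 6 per arm. Power for a 4-minute saving on the interval is 36–55%, 22–35% or 16–24% at SD 3, 4 or 5.
- Read as 5 January 2025: elapsed fraction 0.55 to 0.61; × 60 = 33 to 37 patients; 23 to 27 left, or about 11 to 14 per arm. Power is 85–92%, 61–72% or 43–53%.

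On the first reading the interval could only be reported descriptively.

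**The case for a change.** The strongest case for the concern is that it asks for little. Total time would stay primary, and two clock readings per operation would give supporting evidence on whether a difference arises at the step named in the title. The facts behind it are correct: as described, the arms differ only at the base, and no listed outcome times that step. If the step times vary independently, the total must have a larger SD than the step alone. With an assumed 5-minute difference and a base-step SD of 3, power on the step is about 100%, against 91%, 46% or 24% on the total when the other steps have SD 5, 10 or 15.

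What stands is that a well-defined step time could help interpretation, and that a difference in total time should be read as a difference between the procedures as performed. What does not stand is that leaving it out makes the plan wrong. Use of the harmonic scalpel elsewhere in Arm A only is conjecture; section 9 does not suggest it. Section 10 lists outcomes, not every item on the case report form, so it does not prove that no step times are recorded. Adding an outcome to a study that already reports ethics approval may also need an amendment and a registry entry, so it costs more than two clock readings.

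**Conclusion.** The concern does not hold. Objective and primary outcome agree, randomisation protects the comparison, and following the protocol as written gives a valid answer to the question it poses. The absence of a base-closure time limits explanation and, to an unknown degree, precision for the base step; the primary result would be the same with or without it. The size of the limitation rests wholly on assumed values: at 30 per arm, power on total time runs from 12% (4-minute saving, SD 20) to over 99% (12-minute saving, SD 10). Even accrual and bracketed dates underlie the estimate of patients still available for timing. A step interval is a design preference that brings its own measurement problem, and not a correction the protocol needs.

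This conclusion reads operative time as the whole operation. The protocol states no start or stop point, but that detail may sit in documents not shown.

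### Does listing appendix position as a secondary outcome create an empty comparison and waste a covariate for operative time?

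*Protocol*

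**What the plan says.** Section 10 of the protocol names one primary outcome, "Operative time (in minutes)", and five secondary outcomes. The first of the five is "Position of appendix (intraoperative)", followed by leak, ileus, surgical site infection and hospital stay.

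The matching secondary objective in section 6 is "To document appendix position intraoperatively". The title is in two parts: "Clinical Profile of Appendicitis and Comparative Study of Harmonic Scalpel (Seal and Cut) Versus Suture Ligation of the Base of Appendix". Section 5 closes its rationale with a general sentence: "This study aims to compare outcomes between these two techniques".

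Section 9 defines the arms. The experimental arm is "Laparoscopic appendectomy using harmonic scalpel to seal and divide appendix base" and the comparator is "Laparoscopic appendectomy with intracorporeal suture ligation of appendix base". Section 8 gives "Sample Size: 60 patients (30 per group)". Section 7 describes computer-based randomisation, names no stratification factor, and masks the participant only. The protocol has no analysis section, so it neither gives position a role in the analysis of operative time nor rules one out.

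**The concern.** An outcome should be something the treatment could change. The position of the appendix is anatomy that exists before the operation, and the two arms differ only at the step where the base is closed. Under randomisation, any difference between arms in true position is therefore chance. A test of it would check only the allocation, and a small p-value there could be misread as an effect of technique.

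There is a second strand. Position could plausibly affect how long the operation takes, and it is recorded for every patient. If it does, it would be more useful as a covariate in the analysis of operative time than as an outcome. With only 30 patients per arm, chance imbalance in such a factor can be sizeable, and adjustment could buy precision. What would be at stake is one uninformative line among the secondary results and some lost efficiency in the primary comparison.

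**Working it through.** **Is a between-arm test of position planned?**

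- Section 6 ties the word for comparison to operative time alone. Complications are to be evaluated, stay assessed and position documented. The verbs alone do not settle the matter, since complications and stay will presumably be compared too, but the one used for position is purely descriptive.
- The title pairs a descriptive profile with the comparison, and position fits the descriptive part.
- Section 5 speaks of comparing outcomes in general. It specifies no test and does not mention position.

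The specific objective is the better guide to intent, and it asks for description.

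**How large could a chance imbalance be?** The input from the protocol is 30 per arm; the prevalence p of a given position category is assumed. The standard error of the between-arm difference in proportions is sqrt(2p(1−p)/30).

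| p (assumed) | SE | 1.96 × SE | Chance of a difference of 20 points or more |
|---|---|---|---|
| 0.30 | 11.8 points | 23.2 points | 9.1% |
| 0.50 | 12.9 points | 25.3 points | 12.1% |
| 0.65 | 12.3 points | 24.1 points | 10.4% |

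**What would that do to operative time?** Assume p = 0.50 and that a difficult position adds 15 minutes; the protocol gives neither figure. The shift at the edge of the 95% range is 0.253 × 15 = 3.8 minutes.

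This shift is not an extra error on top of the stated uncertainty. Under the same assumptions, position adds 15² × 0.5 × 0.5 = 56.25 min² to the within-arm variance. Its share of the variance of the difference in means is 2 × 56.25/30 = 3.75 min², and 1.96 × sqrt(3.75) = 3.8 minutes. The same 3.8 minutes is thus already counted in the unadjusted standard error. If position explains a share R² of the variance, the total within-arm variance is 56.25/R², and the unadjusted 95% half-width is 1.96 × sqrt(2 × 56.25/(30 × R²)): 12.0 minutes for R² = 0.10, 8.5 for 0.20 and 6.9 for 0.30. The shift lies inside each of these.

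**What could adjustment gain?** The protocol states no alpha, power, SD or target difference, so its total of 60 can be neither reproduced nor refuted. Assuming two-sided 0.05 and 80% power, the normal approximation gives a detectable difference of (1.960 + 0.842) × sqrt(2/30) = 0.723 SD (0.736 SD with the t distribution). Adjustment multiplies this by sqrt(1−R²).

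| R² (assumed) | Detectable difference | Power for 0.723 SD | Equivalent sample size, 1/(1−R²) |
|---|---|---|---|
| 0 | 0.723 SD | 80.0% | 1.00 |
| 0.05 | 0.705 SD | 82.0% | 1.05 |
| 0.10 | 0.686 SD | 84.0% | 1.11 |
| 0.20 | 0.647 SD | 87.9% | 1.25 |
| 0.30 | 0.605 SD | 91.7% | 1.43 |

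The gain runs from nothing to about 12 points of power, and nothing in the protocol shows where in that range the trial would lie.

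**The case for a change.** The best case for a change is that outcome classification is settled in the protocol, not in a later analysis plan, and that sections 5 and 10 read together do place position among the things to be compared. Moving it to the operative characteristics would be a matter of wording, would need no new data, and would bring section 10 into line with section 6.

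The point about the label stands: position is not a treatment outcome. The consequence does not follow. A table of position by arm is what one would produce under either heading, and a reader would recognise it as a description of the patients. No error rate is allotted to the secondary outcomes in this protocol, so position takes nothing from the others.

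The covariate argument is weaker. That position goes unused cannot be shown, because the choice of covariates is commonly left to the analysis plan. Nor would an adjusted primary model be a plain improvement:

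- Position is classified during surgery, and only the participant is masked. If the operator knows the arm when recording it, the recorded value need not be independent of treatment, although the anatomy is.
- The protocol defines no grouping of positions, so the covariate would have to be constructed.
- Section 13 gives a start of April 2024 and the document is dated 01/05/2025, so a new primary model might be chosen after data had accrued.

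**Conclusion.** No change follows. The heading under which position appears is imprecise, but the stated objective is to document it, no test is specified, and relabelling would alter no result, sample size or error rate. An analyst would sensibly summarise position overall and by arm and draw no treatment conclusion from it.

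The suggested loss in the primary analysis is not established. The imbalance of up to about 25 points, the shift of 3.8 minutes and the gain of 2 to 12 points of power are correct arithmetic. They rest on an assumed prevalence, an assumed 15-minute effect and an assumed R² of 0.05 to 0.30, none of which the protocol supplies. Whatever the true values, the unadjusted randomised comparison of operative time is valid and its standard error already includes the chance imbalance. Adjusting for position is an optional choice for the analysis plan. This conclusion assumes that position is reported descriptively, as section 6 indicates. If a between-arm test were reported after all, it would be uninformative but would leave the primary result untouched.

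### Leak, the only listed outcome that directly measures failure of the base closure, is counted to day 7, although surgical site infection has to be followed to day 30

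*Protocol*

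**What the plan says.** Section 10 of the Protocol (Outcome Measures) gives each postoperative complication its own window. Leak is "Postoperative leak (within 7 days", ileus is limited to 3 days, and infection is "Surgical site infection (within 30 days". No reason is given for any of these limits, and neither leak nor surgical site infection (SSI) is defined.

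Other sections bear on the point:

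- Section 5 (Background and Rationale) describes "secure closure of the appendix base being a critical step".
- Section 6 (Study Objectives) sets the secondary objective "To evaluate postoperative complications (leak, ileus, SSI", without a time limit.
- Section 7 (Study Design) states "Masking: Single (Participant", so surgeons and assessors may know the allocation.
- Section 8 (Participants) plans 60 patients, 30 per group.
- Section 9 (Interventions) separates the arms only by the handling of the base: harmonic sealing and division against intracorporeal suture ligation.
- Section 13 (Timeline) has "Study Start: [April 2024", and the document closes with "Date- 01/05/2025". The trial was therefore already under way when this text was dated.

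**The concern.** The trial compares two ways of closing the appendix base. Of the listed outcomes, operative time, appendix position, ileus, SSI and hospital stay do not measure directly whether the closure held. Leak does. Yet its window is shorter than the follow-up that the Protocol needs anyway for SSI.

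Different windows for different complications are not in themselves an error, and no contradiction is alleged. The weakness is that follow-up already implied by one outcome is not used for the outcome closest to the technique under test. A late leak might be recorded under SSI if SSI includes deep infection, but the Protocol does not say so, and even then it would stay out of the leak count.

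At stake is what the trial can say about the security of the closure. The reported leak count may be lower than follow-up to day 30 would show, and any safety statement based on it covers 7 days only.

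**Working it through.** **The windows.** Leak is counted to day 7 and SSI to day 30. The uncovered period for leak is days 8 to 30, which is 23 of 30 days (23/30 = 77%). Under the stated definition, a leak first found in that period does not enter the leak outcome. This step needs no assumption. The Protocol has no visit schedule, but an SSI outcome to day 30 cannot be measured without some contact or record check up to that day.

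**How many leaks could be missed.** The Protocol gives no figure to reproduce. The leak risk *r* (to day 30) and the share *s* of leaks first found after day 7 are assumptions; *n* = 60 is from section 8.

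- Expected missed leaks = 60 × *r* × *s*
- Chance of missing at least one = 1 − (1 − *r* × *s*)^60

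| Assumed *r* | Assumed *s* | Expected missed | Chance of missing at least one |
|---|---|---|---|
| 1% | 10% | 60 × 0.01 × 0.10 = 0.06 | 1 − 0.999^60 = 5.8% |
| 3% | 25% | 60 × 0.03 × 0.25 = 0.45 | 1 − 0.9925^60 = 36.4% |
| 5% | 50% | 60 × 0.05 × 0.50 = 1.5 | 1 − 0.975^60 = 78.1% |

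The last row pairs the two highest assumed values and is an upper end, not an expectation.

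**What one missed leak does to an arm's result.** With 30 patients per arm and exact (Clopper-Pearson) 95% intervals:

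- 1/30 = 3.3%, interval 0.1% to 17.2%
- 0/30 = 0%, interval 0% to 11.6% (upper limit 1 − 0.025^(1/30))

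**What it does to a test between arms.** Fisher's exact test, two-sided, 30 per arm:

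- 1 v 0 leaks: p = 1.00
- 2 v 0 leaks: p = 2 × 435/1770 = 0.49

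One or two extra leaks would not change a test conclusion in these cases. The effect is on the reported count and its interval.

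**How far the trial had run.** Assume a start on 1 April 2024 and completion between 1 and 31 July 2025, a total of 456 to 486 days. If the document date means 1 May 2025, 395 days had passed (395/486 = 81% to 395/456 = 87%). If it means 5 January 2025, 279 days had passed (279/486 = 57% to 279/456 = 61%). The timeline entries are bracketed and the completion entry reads "Estimated Completion: [e.g., July 2025", so these shares are rough. They show only that many patients may already have been treated.

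**The case against.** The best case for leaving the window alone has four parts.

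1. **Nothing is misstated.** Each complication has an explicit window, section 6 sets no limit that section 10 breaks, and a reader of the outcome label can see that it covers 7 days. This is true, and it is why the point is a design weakness and not an error. It does not bring a late leak into the leak count.

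2. **Late leaks may be too rare to matter.** Section 8 admits only uncomplicated appendicitis and excludes perforated or gangrenous cases. The assumed range spans 25-fold (0.06 to 1.5), so it cannot separate a negligible gap from a material one. This stands: the Protocol cannot settle the size.

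3. **The consequence is small.** The primary outcome is unaffected, no test result turns on the point, and with 30 per arm neither window gives a precise estimate of closure safety. This also stands, and it limits the weight of the point.

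4. **The later data may be poorer.** The form of the day-30 contact is not described, and a wound check or a call may detect leaks less well than observation in hospital. A secondary outcome added late, in a trial where only the participant is masked, carries its own risk. This stands as a reason for care in making the change. It is also a reason to keep the 7-day count beside the new one.

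**Conclusion.** The concern holds. As section 10 is written, a leak first found on days 8 to 30 falls outside the leak outcome. That conclusion rests on the stated windows alone.

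The size rests on assumed values: 0.06 to 1.5 missed leaks among 60 patients, with a middle case of 0.45 and a 36.4% chance of missing at least one. The Protocol cannot show how many would be missed or whether the number would differ between arms, and no direction of bias is claimed. The comparison of operative time is unaffected.

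This is an inexpensive improvement that should be made. It is not a flaw that undermines the trial.

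**What to change.** Keep the 7-day leak outcome in section 10 unchanged and add leak within 30 days as a further secondary outcome, ascertained at whatever contact is used for the 30-day SSI outcome. In addition:

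- Apply the same written criteria for leak in both arms, since only the participant is masked.
- Report the 7-day and 30-day counts by arm with exact 95% intervals.
- State any event that is counted both as leak and as SSI.
- Record the addition as a dated amendment made without reference to outcome data by arm.
- For patients already treated, state how leak status to day 30 was obtained and how many lack it.

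The cost is one outcome line and one extra item at the day-30 contact. The downsides are possible gaps in late data for patients already treated, possibly weaker detection than in hospital, and the need to disclose a secondary outcome added late.
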